	
All patients enrolled in the DEFENDO Study who are not meeting exclusion criteria and/or are not lost to follow-up will be eligible for the DEFENDO Long-Term Follow-up Study.
 
During the DEFENDO Long-Term Follow-up Study, the patients may be treated at the physician's discretion. Any concomitant treatment must be documented. If warranted for patient safety, the Investigator may elect to see the patient at an Unscheduled Visit(s) to evaluate the patient.

Number of Patients	Up to 37
Main Criteria for Inclusion/Exclusion	
Inclusion Criteria - To be eligible for inclusion into this study, each patient must fulfil the following inclusion criteria:
 
 1. Previously enrolled in the DEFENDO Study. 2. Satisfy all Informed Consent requirements. 
 • The patient and/or his/her legal representative has read, signed, and dated the IRB approved Informed Consent document before any study-related procedures are performed. 3. Must have the ability and willingness to comply with study procedures. 
Exclusion Criteria - Patients who meet any of the following criteria are NOT eligible for inclusion in the study:
 
 1. Participating in another study that involves treating the study eye. 
 a. Participation in non-ocular studies is acceptable provided that the treatment is not considered to be confounding with the DEFENDO Long-Term Follow-up Study, in the opinion of the Investigator.
Duration of Treatment	No study treatment will be provided
Reference product, Dosage and Mode of Administration	N/A

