1.1 Study Objectives

Primary Objective

The primary objectives are to evaluate the long-term safety and efficacy (corneal epithelial healing) of OXERVATE™ 0.002% (20 mcg/mL) cenegermin-bk bj ophthalmic solution in Stage 1 Neurotrophic Keratitis (NK) patients who enrolled in the DEFENDO Study.

Secondary Objective

The secondary objectives are to evaluate the long-term efficacy of OXERVATE™ 0.002% (20 mcg/mL) cenegermin-bk bj ophthalmic solution in terms of Corneal Sensitivity, Schirmer I Test, Tear Film Break Up Time (TFBUT), Best Corrected Distance Visual Acuity (BCDVA), and Quality of Life at 24 and 30 months.

CCI

CCI

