11 questions are included in the Emotional Well-Being score. Question 21 (IDLEMO12) is excluded from calculation. If 50% (5) or fewer of the 11 questions used in the calculation of Emotional Well-Being score have missing item score, then the scale score is calculated by multiplying the mean of the non-missing item scores by 25. If 6 or more of the 11 item scores are missing, then the scale score is not calculated and should be set at missing. Multiplying by 25 transforms the scale score to a 0 to 100 scale, with 0 reflecting the worst level of emotional well-being measurable by the scale and 100 reflecting the best.

1.c Work

Work	Used in calculation of domain score?
22. Are you currently working?	-
23. Feeling distracted	Yes
24. Feeling like I couldn't concentrate	Yes
25. Having to take a break from work	Yes
26. Having to change the way I work (such as the way I read, look at a computer, or work outside)	Yes
27. Having to change my work environment (such as how close I am to an air conditioning or heating vent)	Yes

Response for question 22	Original response code	Item score
Yes	1	1
No	2	0

Response for questions 23 to 27	Original response code	Item score If Response for question 22=0	Item score If Response for question 22=1
None of the time	1	Missing	4
A little of the time	2	Missing	3
Some of the time	3	Missing	2
Most of the time	4	Missing	1
All of the time	5	Missing	0

5 questions are included in the Work Limitations domain. If 50% (2) or fewer of the 5 questions used in the calculation of the Work Limitations score have missing item scores, then the scale score is calculated by multiplying the mean of the non-missing item scores by 25. If 3 or more of the 5 item scores are missing, then the scale score is not calculated and should be set to missing. Multiplying by 25 transforms the scale score to a 0 to 100 scale, with 0 reflecting the greatest degree of limitation at work measurable by the scale and 100 reflecting the least limitation at work.

Module 2:

Dry eye Treatment satisfaction & Bother module (10 questions) comprising 2 QoL domains: 2.a “Satisfaction with Treatment Effectiveness” and 2.b “Treatment-Related Bother/Inconvenience”.

2.a Satisfaction with Treatment Effectiveness

Satisfaction with Treatment Effectiveness	Used in calculation of domain score?
1. OVER THE LAST TWO WEEKS , how often did you use treatment for your dry eyes?	-
2. I was happy with how quickly my treatments worked	Yes

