3. I was happy with how long the effects of my treatments lasted	Yes
4. The treatments I used completely eliminated my dry eye symptoms	Yes
5. The treatments I used relieved most of my dry eye symptoms	Yes

Response for question 1	Original response code	Item score
None of the time	1	0
A little of the time	2	1
Some of the time	3	2
Most of the time	4	3
All of the time	5	4

Response for questions 2 to 5	Original response code	Item score If Response for question 1 = 0	Item score If Response for question 1 > 0 or missing
None of the time	1	Missing	0
A little of the time	2	Missing	1
Some of the time	3	Missing	2
Most of the time	4	Missing	3
All of the time	5	Missing	4

4 questions are included in the Treatment Satisfaction/Happiness scale score. If 50% (2) or fewer of the 4 questions used in the calculation of Treatment Satisfaction/Happiness score have a missing item score, then the scale score is calculated by multiplying the mean of the non-missing item score by 25. If 3 or

more of the 4 item scores are missing, then the scale score is not calculated and should be missing. Multiplying by 25 transforms the scale score to a 0 to 100 scale, with 0 reflecting the lowest level of satisfaction/happiness with treatment measurable by the scale and 100 reflecting the highest level of satisfaction/happiness with treatment.

2.b Treatment-Related Bother/Inconvenience

Treatment-Related Bother/Inconvenience	Used in calculation of domain score?
6. I was bothered by how often I had to use dry eye treatments	Yes
7. Do you ever use eye drops to treat your dry eyes?	-
8. I was bothered by blurriness shortly after using my eye drops	Yes
9. I was embarrassed when I had to use my eye drops	Yes
10. I felt like I could not go anywhere without my eye drops	Yes

Response for question 7	Original response code	Item score
Yes	1	1
No	2	0

Response for question 6, 8 to 10	Original response code	Item score If Response for question 1 = 0	Item score If Response for question 1 > 0
None of the time	1	Missing	4
A little of the time	2	Missing	3
Some of the time	3	Missing	2
Most of the time	4	Missing	1
All of the time	5	Missing	0

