All questions are included in the Symptom Bother scale score. If 50% (10) or fewer of the 20 questions used in the calculation of Symptom Bother scale score have missing item scores, then the scale score is calculated by multiplying the mean of the non-missing item score by 25. If 11 or more of the 20 item scores are missing, then the scale score is not calculated and should be set at missing. Multiplying by 25 transforms the scale score to a 0 to 100 scale, with 0 reflecting the greatest degree of treatment related bother measurable by the scale and 100 reflecting the lowest degree of treatment-related bother.

Change from baseline and from week 8 of above defined subscores will be summarized as a continuous variable at each visit, and mean changes from baseline and from week 8 of all the subscores will be graphically presented (e.g., radar plot) for each visit.

- EQ-5D-5L change from baseline and Week 8 at Month 24 and Month 30

Change from baseline and from week 8 of each dimension score and overall score of health today will be summarized as a continuous variable at each visit, and mean changes from baseline and from week 8 of all the dimension scores will be graphically presented (e.g., radar plot) for each visit.

[REDACTED]

[REDACTED]

[REDACTED]

[REDACTED]

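### IDEEL subscores 2.a and 2.b rate the patient's current dry-eye treatment, yet SAP 5 presents their changes with the other subscores as long-term OXERVATE efficacy

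*SAP*

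**What the plan says.** The secondary objective in SAP 1.1 reads "The secondary objectives are to evaluate the long-term efficacy of OXERVATE" and names quality of life among the outcomes. Protocol 8.1 makes change in the IDEEL a study endpoint without singling out modules.

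SAP 5 scores the IDEEL as three modules. Module 2 opens with a question on the last two weeks, "how often did you use treatment for your dry eyes". Its scored items are worded about the patient's treatments in general. An example from 2.a is "I was happy with how long the effects of my treatments lasted", and one from 2.b is "I was bothered by how often I had to use dry eye treatments". No item names OXERVATE.

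The scoring keys for both subscores have a column headed "Item score If Response for question 1 = 0", in which every scored item is missing. For 2.a the scale rule is that if three or "more of the 4 item scores are missing, then the scale score is not calculated and should be missing"; 2.b has the same rule.

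SAP 5 then treats all subscores alike: "Change from baseline and from week 8 of above defined subscores will be summarized as a continuous variable at each visit". They go into Table 14.2.6 and the radar plots in Figures 14.2.1.1 and 14.2.1.2. On treatment during follow-up, the Protocol synopsis says "No study treatment will be provided". Protocol 6.2 allows any standard of care the Investigator chooses, including commercially available OXERVATE.

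**The concern.** A change score is informative about OXERVATE only if the same thing is rated at both visits and the rating bears on what OXERVATE did. For 2.a and 2.b neither is assured. The thing rated is the treatment of the last two weeks, which can differ between baseline, Week 8, Month 24 and Month 30. A shift may reflect a change of product, not a change in the eye.

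The scores also exist only for patients who report some treatment use. Anyone who answers 'None of the time' to question 1 leaves both scores, and the analysis uses observed cases without imputation. The output would not show whether a patient is absent because no treatment was used or because the form was incomplete.

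At stake is the reading of two of the six IDEEL subscores in the efficacy table and plots, where a reader would naturally take them as quality-of-life benefit or loss from OXERVATE.

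**Working it through.** The plan gives no rate or effect size on this point. Its own figures are the 0 to 100 scale range and the missing-item threshold, so I checked those first.

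**1. Scoring rule (SAP 5, Module 2).** Score = 25 × mean of the non-missing item scores (each 0 to 4). The score is missing if 3 or more of the 4 items are missing.
- All items at 0: 25 × 0 = 0. All items at 4: 25 × 4 = 100. The stated range is reproduced for both subscores.
- Two items missing, the others 2 and 3: 25 × (2 + 3)/2 = 62.5, so a score is given. With three missing there is no score.
- Question 1 scored 0: all 4 items are missing, and 4 ≥ 3, so 2.a and 2.b are both missing whatever else the patient answered.

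**2. What is rated at each visit.** SAP 2.2 lists Week 8 as a treatment visit, and Protocol 3 describes six-times-daily dosing for 8 weeks. At Months 24 and 30 no study product is given and any standard of care may be in use. SAP 2.7 plans no subgroups, so the IDEEL analysis does not separate patients by current product. Suppose a patient scores 75 for one product at Week 8 and 50 for another at Month 24 (assumed values). The change is 50 − 75 = −25, although the two scores rate different things.

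**3. Sensitivity of one item.** If only item 6 moves from an item score of 1 to 4, subscore 2.b rises by (4 − 1)/4 × 25 = 18.75 points. This shows the mechanism and is not a forecast. A patient who stops all treatment is set to missing and cannot contribute such a gain.

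**4. How many change scores could exist.** Expected pairs = N × u, where u is the share using treatment at both visits. The documents do not give u, and 37 is the ceiling on N.

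| N | u = 0.8 | u = 0.6 | u = 0.4 |
|---|---|---|---|
| 37 | 29.6 | 22.2 | 14.8 |
| 20 (assumed) | 16 | 12 | 8 |

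**5. By-visit means against paired changes.** Assume 37 patients, all with a score at baseline. Fifteen score 75 and later report no treatment use; 22 score 25 and do not change.
- Baseline mean: (15 × 75 + 22 × 25)/37 = 1675/37 = 45.3 (n = 37).
- Month 24 mean: 25 (n = 22).
- Paired mean change: 0 (n = 22).

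The drop from 45.3 to 25 comes entirely from who is left. The paired change avoids it in this example but says nothing about the 15 who left.

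**6. What the planned output would reveal.** SAP 2.8 reports n with data and SAP 2.10 reports one 'Missing' count. Neither splits no treatment use from unanswered items. The 2.b key also has no column for an unanswered question 1, whereas the 2.a key does.

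**The case against.** Several counter-arguments have force.

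- **The analyses are exploratory.** SAP 2.9 and 5 say so for all efficacy results, and no primary endpoint, sample size or safety conclusion depends on Module 2. This stands and keeps severity low. It does not make a score address an objective that it does not measure.
- **Attrition would be visible.** The n, the 'Missing' count and Listing 16.2.6.6 would show it, and the affected patients stay in the full analysis set and in every other endpoint. This partly stands, but the reason for the missing score would still need digging out of the listing.
- **The gate may be the instrument's own rule.** The SAP cites the IDEEL user manual, and a satisfaction score for a non-user is arguably not applicable. I accept this. The scoring is not in dispute, only the efficacy reading.
- **Deleting prespecified subscores could look selective.** The protocol endpoint is the IDEEL without exclusions, SAP 9 plans no changes from protocol, and the parent data already exist. This stands against deletion. It does not stand against separate presentation.

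A reader might infer more than the documents support:
- *That those who drop out are the patients doing best.* Question 1 asks about use, not need. Protocol 3.3.1 also lists options, such as therapeutic lenses, that a patient may not count as dry-eye treatment.
- *That Week 8 scores are ratings of OXERVATE, so bother must improve once the drops stop.* OXERVATE is described as a treatment for neurotrophic keratitis while the items ask about dry eye. Nothing shows how patients answered, or what else they were using at baseline and Week 8.
- *That OXERVATE plays no part at Months 24 and 30.* Commercial use is allowed, so some later ratings may be of OXERVATE.

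**Conclusion.** The point holds as a mismatch between what 2.a and 2.b measure and how they are presented. It follows from the item wording, the gate on question 1 and the absence of study product, all of which are explicit. No section of the SAP exempts Module 2 or qualifies how it should be read.

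It affects two of six IDEEL subscores under one secondary objective. Direction and size of any distortion are unknown. The 18.75 points, the −25 and the 45.3 to 25 shift rest on assumed responses, and the counts of evaluable pairs rest on an assumed share of treatment users. The documents do not support a claim that the quality-of-life results will be biased by a given amount, or that the gate itself biases the paired change. Severity is low. The change is still worth making, because it prevents a misreading that the single 'Missing' category would leave in place.

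**What to change.** In SAP 5 and the table and figure shells:

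1. Present 2.a and 2.b in a separate table labelled 'ratings of current dry-eye treatment, not evidence of lasting OXERVATE effect', and take them out of Figures 14.2.1.1 and 14.2.1.2.
2. At each visit show n (%) answering 'None of the time' to question 1, labelled 'no treatment use reported', separately from unanswered items. State how 2.b is scored when question 1 itself is unanswered.
3. If changes in 2.a and 2.b are kept, show them only for patients with scores at both visits, with that n. Do not compare by-visit means computed on different patients.
4. Base the quality-of-life efficacy reading on Modules 1 and 3, noting that 1.c (Work) applies only to patients who are working. Before relying on Module 3, settle its direction: its item scores rise with bother, but the text beneath the key says that 0 is the greatest bother.

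Cost: SAP wording, one extra table and two fewer axes on the plots. No new data are needed, and both subscores are still reported.

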6 ANALYSIS OF SAFETY

All safety parameters will be summarized based on the FAS Population.

6.1 Adverse Events

Adverse events will be classified according to the MedDRA to the levels of SOC and PT. SOC will be sorted alphabetically and PT within each SOC will be sorted by overall descending order of frequency. All events in the clinical database regardless of when they occurred will be provided in data listings.

The number and percentage of subjects experiencing one or more events will be tabulated by SOC and PT. In addition, similar tables by SOC and PT will be displayed further by maximum severity, and by closest relationship to treatment. For summary, the AEs with relationship to treatment reported as "None" or

“Unlikely” are considered “Not Related”, and “Possible”, “Probable”, or “Highly Probable” are considered “Related”.

Summary tables will be prepared also for the number and percentage of subjects experiencing one or more events during the entire extended follow-up period.

In summary tables for ocular adverse events, AEs occurring in both eyes will be summarized once at the greater severity or closer relationship to study drug.

A listing of serious AEs (SAEs) will be also provided.

A glossary listing that shows the verbatim terms assigned to each SOC and PT will be provided.

6.2 Slit Lamp Examination

Categorical results of slit lamp examination will be summarized for each parameter in a frequency table for study eye and treated non-study eye by visit (i.e., baseline, Week 8, Month 24 and Month 30). Following parameters will be included: Anterior Chamber Cells, Anterior Chamber Flare, Anterior Chamber Other Abnormal Finding, Conjunctiva Edema, Conjunctiva Bulbar Erythema, Conjunctiva Other Abnormal Finding, Cornea Edema, Cornea Endothelial Changes, Cornea Epithelial Changes, Cornea Other Abnormal Finding, Iris, Iris Other Abnormal Finding, Lashes, Lens, Lens Other Abnormal Finding, Eyelid Edema, Eyelid Erythema, Eyelid Other Abnormal Finding, Sclera, Sclera Other Abnormal Finding.

6.3 External Ocular Examination

Categorical results of external ocular examination will be summarized for each parameter in a frequency table for study eye and treated non-study eye by visit (i.e., baseline, Week 8, Month 24 and Month 30). The following parameters will be included: Motility of extraocular muscles, Appearance of eyelids, Specific mechanism.

7 DETERMINATION OF SAMPLE SIZE

The sample size for this study is not based on hypothesis-testing and power considerations but is determined by the number of patients from the DEFENDO Study who will rollover to the DEFENDO Long-Term Follow-up Study. The DEFENDO Study enrolled a total of 37 patients.

8 PLANNED INTERIM ANALYSIS

A descriptive interim analysis will be carried out as soon as the last patient is enrolled in the study. The purpose of this analysis will be administrative. Since the study has an exploratory nature and no formal hypothesis test is planned, no adjustment is needed for the final analysis due to the performance of an administrative interim analysis.

9 CHANGES FROM PROTOCOL

No changes from protocol are planned.

Appendix 1: Schedule of Evaluations (from Protocol)

Procedures	Visit 1	Visit 2
	24-27 Months	30-33 Months
24-Month Study Visit	30-Month Study Visit / End of Study	
Inclusion/Exclusion Criteria	X	
ICF/HIPAA	X	
Record AEs	X	X
Prior and Concomitant Medications	X	X
IDEEL	X	X
EQ-5D-5L	X	X
BCDVA	X	X
External Ocular Examination	X	X
Slit-Lamp Examination	X	X
Corneal Photography Without Fluorescein	X	X
Instillation of Fluorescein	X	X
TFBUT	X	X
Corneal Photography with Fluorescein	X	X
Corneal Sensitivity Testing	X	X
Schirmer Test (w/o Anesthesia)	X	X

CCI

Appendix 2 Tables, Listing, and Figures**List of tables**

Table Number	Table Title	Analysis Population
14.1.1	Analysis Populations	
14.1.2	Subject Disposition	Full Analysis Set
14.1.3	Visit Participation	Full Analysis Set
14.1.4	Demographics	Full Analysis Set
14.1.5.1	Medical History	Full Analysis Set
14.1.5.2	Ocular History	Full Analysis Set
CCI		
14.1.6.3	Non-ocular Medications during Extended Follow-up	Full Analysis Set
14.2.1.1	Percentage of Patients who Achieved Epithelial Healing at Week 8 and Had Healed during Extended Follow-up	Full Analysis Set
14.2.1.2	Percentage of Patients who Did Not Achieve Epithelial Healing at Week 8 and Had Healing during Extended Follow-up	Full Analysis Set
14.2.2.1	Corneal Sensitivity Changes from Baseline and Week 8 during Extended Follow-up	Full Analysis Set
14.2.2.2	Percentage of Patients Who Improved in Corneal Sensitivity from Baseline to Week 8 and Still Had Improvement during Extended Follow-up	Full Analysis Set
14.2.2.3	Percentage of Patients Who Did Not Improve from Baseline in Corneal Sensitivity at Week 8 and Had Improvement during Extended Follow-up	Full Analysis Set
14.2.3	Schirmer I Change from Baseline and Week 8 during Extended Follow-up	Full Analysis Set
14.2.4	TFBUT Change from Baseline and Week 8 during Extended Follow-up	Full Analysis Set
14.2.5.1	BCDVA Change from Baseline and Week 8 during Extended Follow-up	Full Analysis Set
14.2.5.2	Percentage of Patients Achieved a 15- letter Gain from Baseline in BCDVA during Extended Follow-up	Full Analysis Set
14.2.5.3	Percentage of Patients Achieved a 15- letter Gain from Week 8 in BCDVA during Extended Follow-up	Full Analysis Set
14.2.6	IDEEL Change from Baseline and Week 8 during Extended Follow-up	Full Analysis Set
14.2.7	EQ-5D-5L Change from Baseline and Week 8 during Extended Follow-up	Full Analysis Set
CCI		
14.3.1.1	Summary of Adverse Events during Extended Follow-up	Full Analysis Set
14.3.1.2	Frequency of Adverse Events by System Organ Class and Preferred Term during Extended Follow-up	Full Analysis Set
14.3.1.3	Frequency of Adverse Events by System Organ Class and Preferred Term and by Maximum Severity during Extended Follow-up	Full Analysis Set
14.3.1.4	Frequency of Adverse Events by System Organ Class and Preferred Term and by Closest Relatedness during Extended Follow-up	Full Analysis Set

Table Number	Table Title	Analysis Population
14.3.1.5	Adverse Event - MedDRA Glossary	Full Analysis Set
14.3.2	Listing of Serious Adverse Events during Extended Follow-up	Full Analysis Set
14.3.3	Frequency Summary of Slit-Lamp Examination Results during Extended Follow-up	Full Analysis Set
14.3.4	Frequency Summary of External Ocular Examination Results during Extended Follow-up	Full Analysis Set

List of listings

Listing Number	Listing Title	Analysis Population
16.2.1.1	Subject Disposition	Full Analysis Set
16.2.1.2	Analysis Visits	Full Analysis Set
16.2.2.1	Inclusion and Exclusion Criteria Exceptions	Full Analysis Set
16.2.2.2	Protocol Deviations	Full Analysis Set
16.2.3	Analysis Populations	Full Analysis Set
16.2.4.1	Demographics	Full Analysis Set
16.2.4.2	Etiology of Neurotrophic Keratitis	Full Analysis Set
16.2.4.3	Medical and ocular history	Full Analysis Set
16.2.5	Concomitant Medications	Full Analysis Set
16.2.6.1	Fluorescein Corneal Staining and Epithelial Healing	Full Analysis Set
16.2.6.2	Corneal Sensitivity Testing	Full Analysis Set
16.2.6.3	Best Corrected Distance Visual Acuity (BCDVA)	Full Analysis Set
16.2.6.4	Tear Film Break-Up Time (TFBUT)	Full Analysis Set
16.2.6.5	Schirmer Test	Full Analysis Set
16.2.6.6	Impact of Dry Eye on Everyday Life (IDEEL)	Full Analysis Set
16.2.6.7	EQ-5D-5L	Full Analysis Set
CCI		
16.2.7	Adverse Events	Full Analysis Set
16.2.8.1	Slit-Lamp Examination	Full Analysis Set
16.2.8.2	External Ocular Examination	Full Analysis Set

List of figures

Figure Number	Figure Title	Analysis Population
14.2.1.1	Radar Plot of Mean Change from Baseline of IDEEL Subscores during Extended Follow-up	Full Analysis Set
14.2.1.2	Radar Plot of Mean Change from Week 8 of IDEEL Subscores during Extended Follow-up	Full Analysis Set
14.2.2.1	Radar Plot of Mean Change from Baseline of EQ-5D-5L Dimensions during Extended Follow-up	Full Analysis Set
14.2.2.2	Radar Plot of Mean Change from Week 8 of EQ-5D-5L Dimensions during Extended Follow-up	Full Analysis Set

Certificate Of Completion

Envelope Id: PPD

Status: Completed

Subject: Complete with DocuSign: NGF0122_SAP 2.0_Final 22Mar2024.pdf

Source Envelope:

Document Pages: 28

Signatures: 2

Envelope Originator:

Certificate Pages: 5

Initials: 0

PPD

AutoNav: Enabled

PPD

Enveloped Stamping: Disabled

PPD

Time Zone: (UTC-05:00) Eastern Time (US & Canada)

PPD

PPD

PPD

Record Tracking

Status: Original

Holder: PPD

Location: DocuSign

3/22/2024 1:20:20 PM

PPD

Signer Events**Signature****Timestamp**

PPD

PPPD

Sent: 3/22/2024 1:23:47 PM

Security Level: Email, Account Authentication
